Based on the randomised trials showing benefit of radiotherapy with combined hormone- and radiotherapy compared to hormone therapy only (9,13,14), 3 months pre-irradiation castration is standard for high-risk patients in many institutions (7). Studies have addressed weakening MRI signals and PSMA PET-uptake after castration (60,61). However, there is not enough data to guide us to the optimal imaging to define intra-prostatic lesions in patients who are treated with a combination

of medical castration and radiotherapy. Currently this topic is being investigated in a phase 2 study (Danish Ethical Committee 2303938), conducted by the research group to prepare for the present study.

Additional improvements in delivery, such as MRI based image guidance, improved CT based image guidance, or adaption of the daily dose plan to the anatomy of the day etc. may improve outcomes further (58,62). If participating centers implement follow local adaptive strategies for adaptation due to anatomical changes, the center must document the procedures.

Study design

Statistical considerations

The reference schedule is 20 fractions, 5 fractions per week, without boost. For this reference schedule we assume the following outcomes of relevance to the statistical sample size calculation:

- 5-year biochemical control: 87%
- 5-year freedom from distant metastasis: 90% with sensitivity analysis 85%-90% 5 year OS: 82%.
- Prevalence of grade 2 or worse gastrointestinal(GI) toxicity: 10% at ~1 year
- Prevalence of grade 2 or worse genitourinary(GU) events: 20% at ~1 year

Dropout is assumed to be dominated by death from other causes. The expected OS of 82% yields a dropout rate of $\eta=0.039$ when assessing endpoints where death is a competing event (Such as freedom from distant metastasis). We account for this dropout in the calculations below.

Table showing overall design

		Fractionation trial Trial tests for non-inferiority of short fractionation	
		12 fractions	20 fractions
Boost trial Trial tests for superiority of focal boost	Boost	Boost: 60 Gy/12 fractions (EQD2=110 Gy) Prostate: 50 Gy/12 fractions (EQD2=80 Gy) Pelvic: 37 Gy/12 fractions (EQD2=48 Gy)	Boost: 75 Gy/20 fractions (EQD2=110 Gy) Prostate: 60 Gy/20 fractions (EQD2=77 Gy) Pelvic: 45 Gy/20 fractions (EQD2=48 Gy)
	No boost	Prostate: 50 Gy/12 fractions (EQD2=80 Gy) Pelvic: 37 Gy/12 fractions (EQD2=48 Gy)	Prostate: 60 Gy/20 fractions (EQD2=77 Gy) Pelvic: 45 Gy/20 fractions (EQD2=48 Gy)

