The potential advantages for a patient participating in the trial is to have fewer fractions in the experimental arms (12 fractions versus the standard arm of 20 fractions), and to reduce the risk of distant metastases by increasing the dose to the intraprostatic tumor lesion.

Potential risks for the patient

The potential disadvantage for the patient is an increased risk of late side effects from the lower urinary tract and rectum and bowel.

The side effects and risks of curatively intended combined LHRH-treatment, and radiotherapy for prostate cancer is well described and the patients will be informed about the risks before treatment.

We cannot exclude an increased risk of urinary and/or genito-urinary toxicity in the short treatment arm as the primary endpoint is non-inferiority for increased toxicity. A careful collection of recorded toxicity is therefore an important part of the study. An independent data monitoring committee will oversee the data during the study (see paragraph on independent data monitoring committee).

The concept of the study is to test if increased dose to intra prostatic lesions without increased dose to the surrounding organs improves tumour control. For the patients in the boost arm, we will also ensure that dose to urethra is kept the same dose level as the non-boost arm. However, we cannot completely exclude a higher risk of urinary toxicity.

Withdrawal of consent

The participant can withdraw from the trial at any time, and he does not have to give a reason for withdrawal. If he chooses to have standard therapy, this will be external beam radiotherapy according to the current DAPROCA guidelines.

Patients, who for some reason do not receive the allocated therapy, are to be treated at the doctor's discretion. The analysis of data will be according to the intention-to-treat principle. Unless the patient

does not accept it, he is followed as all other patients in the trial regarding the primary and secondary endpoints.

For patients not receiving the allocated therapy or withdrawing from the trial at a later point of time, the date of exit from the trial is registered as also the reason if possible. The patient is informed about the burden of follow up before randomization to minimize withdrawal from the trial. The patient can withdraw from the trial without telling a reason at any time.

Possible benefits for society

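### Intention-to-treat is the only analysis principle stated, with no exception for the 12 v 20 fraction toxicity non-inferiority test, where switching between schedules would favour the claim

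*Protocol*

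**What the plan says.** The overall design table describes the fractionation comparison thus: "Trial tests for non-inferiority of short fractionation". The section *Non-inferiority of short fractionation*, placed under the heading on primary endpoints, sets limits of 15% for GI and 27% for GU events and claims more than 80% power on both with 1,016 patients. *Statistical considerations* gives the 20-fraction reference: "Prevalence of grade 2 or worse gastrointestinal(GI) toxicity: 10% at ~1 year" and "Prevalence of grade 2 or worse genitourinary(GU) events: 20% at ~1 year". *Potential risks for the patient* says of the short arm that "the primary endpoint is non-inferiority for increased toxicity". The *Endpoints* section, by contrast, lists only freedom from distant metastasis as primary. The point below holds whichever status applies.

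*Withdrawal of consent* then deals with departures from allocation. On a patient who withdraws: "If he chooses to have standard therapy, this will be external beam radiotherapy according to the current DAPROCA guidelines". On others: "Patients, who for some reason do not receive the allocated therapy, are to be treated at the doctor's discretion". The next sentence is the analysis rule: "The analysis of data will be according to the intention-to-treat principle". Patients who leave their allocation are still followed for the endpoints unless they decline.

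The protocol contains no per-protocol or adherence-based comparison of the two schedules. The late-toxicity dose-response study is blinded to arm and does not compare schedules.

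**The concern.** In a superiority test, analysing patients as randomised when some received the other treatment pulls the difference towards zero and so works against the claim. That suits the boost question. In a non-inferiority test on toxicity the same pull works for the claim. A patient allocated to 12 fractions but treated in 20 brings 20-fraction toxicity into the 12-fraction group. A patient moved the other way brings 12-fraction toxicity into the reference group. Both shrink the observed excess.

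The number of fractions cannot be hidden from patient or doctor, and the protocol itself provides for patients who "for some reason do not receive the allocated therapy", so some switching is foreseeable. The error at stake is declaring the shorter schedule acceptable on late toxicity when its true excess is as large as the limit. Later patients would bear that error.

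**Working it through.** **Inputs from the protocol.** Reference prevalence p0: 10% GI, 20% GU. Limits: 15% and 27%, so the margins m are 5 and 7 percentage points. Four arms of 254 give n = 508 per schedule.

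**Assumptions.** One-sided alpha of 5% (z = 1.645). The protocol states this level only for the boost test, so 2.5% is also shown. The switching rates are assumed because none is given. Switchers carry the toxicity of the schedule they receive.

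**Step 1: the protocol's own power.** With a true difference of zero, power = Φ(m/SE − z), where SE = √(2·p0(1−p0)/n).
- GI: SE = √(2·0.10·0.90/508) = 0.0188; 0.05/0.0188 − 1.645 = 1.01; power 84.4%.
- GU: SE = √(2·0.20·0.80/508) = 0.0251; 0.07/0.0251 − 1.645 = 1.14; power 87.4%.

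The claim of more than 80% on each endpoint is reproduced at one-sided 5%. At one-sided 2.5% the figures are 75.7% and 79.7%.

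**Step 2: false-claim risk under intention-to-treat.** Put true 12-fraction toxicity at the limit. Let a share c of the 12-fraction group be treated in 20 fractions. The group's rate becomes p12 = (1−c)·limit + c·p0, and the difference as randomised becomes (1−c)·m. The chance of wrongly declaring non-inferiority is Φ((m − (1−c)·m)/SE − z) = Φ(c·m/SE − z), with SE = √(p12(1−p12)/n + p0(1−p0)/n).

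Example, GI, c = 10%: p12 = 0.145; SE = √((0.1240 + 0.0900)/508) = 0.0205; 0.005/0.0205 − 1.645 = −1.40; error 8.1%.

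| Switching (assumed) | GI error | GU error |
|---|---|---|
| None | 5.0% | 5.0% |
| 2%, 12 to 20 only | 5.5% | 5.6% |
| 5%, 12 to 20 only | 6.4% | 6.5% |
| 10%, 12 to 20 only | 8.1% | 8.4% |
| 20%, 12 to 20 only | 12.4% | 13.3% |
| 5% each way | 8.0% | 8.4% |
| 10% each way | 12.3% | 13.2% |

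At one-sided 2.5%, 10% one-way switching gives 4.3% GI and 4.5% GU.

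**Step 3: the same effect as a margin.** With 10% one-way switching, the excess among patients treated as allocated that corresponds to the stated margin is 0.05/0.9 = 5.6 points for GI and 0.07/0.9 = 7.8 points for GU.

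**Step 4: can the trial afford a second set?** At one-sided 5%, 80% power needs 446 (GI) and 404 (GU) per schedule. Of 508, that allows about 12% and 20% exclusions. With 10% excluded from each schedule (457 left), power in that set is about 81% GI and 84% GU.

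**The case against.** **Analysis sets belong in the SAP.** The protocol promises a published SAP before data analysis, and that document could add a supporting analysis without contradicting the protocol. This stands in part: a missing per-protocol definition would be no finding. The point is the rule that the protocol does state. It is general, follows directly on the sentence about off-allocation patients, and exempts nothing. With that as the only principle, an unfavourable second analysis could later be set aside as mere sensitivity.

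**Intention-to-treat is not an error.** It preserves randomisation, and a per-protocol analysis alone invites selection bias. This stands fully. A reader might infer that intention-to-treat is wrong for non-inferiority and should be replaced. The protocol gives no ground for that; the weakness is that it stands alone.

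**The size is unknown.** This also stands. Nothing in the protocol supports 10–20% switching. A 12-fraction course at five fractions a week is short, fewer fractions are presented as an advantage, and patients are told of the follow-up burden beforehand to limit withdrawal. Mainly one-sided switching is possible, not shown.

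**Some switchers would not dilute.** A withdrawing patient is treated by current national guidelines, and *Possible benefits for society* calls 39 fractions the current standard. A move from 20 fractions to a less toxic third schedule would not dilute an excess.

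**Requiring completion of the allocated fractions would be the wrong second set.** This is correct. It would drop patients who stop a 12-fraction course because of toxicity, and so could itself favour non-inferiority.

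**Conclusion.** The point holds conditionally. The only stated analysis principle is anti-conservative for the 12 v 20 toxicity test if patients cross between the two schedules, and no provision guards against that. At 5% one-way switching or less the inflation is small, from an assumed 5% to at most about 6.5%. It reaches 8.1–8.4% at 10% and 12–13% at 20%.

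These figures rest on an assumed alpha, assumed switching rates, true toxicity exactly at the limit, and switchers having the toxicity of the schedule they received. A reader might infer that the error will exceed its nominal level in this trial. The protocol does not support that unconditional reading: it gives neither a switching rate nor a nominal level for this test. The change is still worth making, because it is cheap and the condition for harm cannot be ruled out in advance.

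**What to change.** In *Withdrawal of consent*, keep intention-to-treat for the boost superiority analyses and as one of two analyses of 12 v 20 toxicity. Add the second: patients who started their allocated fractionation schedule, analysed by that schedule, keeping everyone who stopped early, including for toxicity. Define the set by the 12- or 20-fraction schedule to the prostate and not by boost sessions, since the protocol lets the boost be given in fewer fractions on special equipment. State that non-inferiority is claimed only if both analyses meet the criterion, and report the number treated off schedule in each arm.

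Costs: a few sentences and one repeat analysis. Because both analyses must pass, overall power is somewhat below the second-set figures of about 81% GI and 84% GU that apply if 10% are excluded from each schedule. The second set is chosen after randomisation, so some selection bias remains possible; this is why it accompanies intention-to-treat and does not replace it. *Follow-up and Data Collection* lists the prescribed fractionation but does not expressly list the schedule started or the fractions delivered, so one data field may have to be added.

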Appendix A: Radiotherapy Quality Assurance

An internal Quality Assurance (QA) group will be established, consisting of at least two medical physicists and two oncologists selected from the Core Group or Work Packages.

The QA group will review the first patient treated with a focal boost in each fractionation regimen at each center, totaling two patients. The group will evaluate and provide feedback on the delineation of the focal boost, targets, and organs at risk, in accordance with the established consensus guidelines. Additionally, dose planning for these two patients will be reviewed by the QA group prior to the initiation of the first treatment, with detailed feedback provided.

Each participating center is also required to submit its daily imaging and adaptive strategies to the QA group for evaluation and subsequent feedback.

Image data include prospective trial data collection from Rigshospitalet (Ethical approval, VMK case nr. 2303938 approved 21/06-2023). We expect 10 patients to be available with multiparametric or PSMA PET/MRI before the start of hormone treatment and at the start of RT, 3 months later. Image acquisitions will be optimal for comparison of response using the same sequences in the two acquisitions and optimised for RT planning.

The data will be made available for a consensus workshop on target delineation following the model used by other multidisciplinary groups in Denmark using the available infrastructure (82-85). The inter- and intraobserver variability in delineation will be assessed, and guidelines written based on these results and consensus at the workshop.

Finally, a small dataset of 10 patients with weekly MRI during RT (Ethical approval number nr. 91936), available at Rigshospitalet can be used for documenting the delivery precision in the simulated treatments accounting for anatomical variations. Workshops regarding treatment planning and plan quality will be conducted using established national imaging and planning archive (DcmCollab). The consensus plans will serve as a benchmark for the plan complexity that the treatment delivery machines must be able to reproduce. This in turn will form the basis of the QA-program across participating institutions.

Imaging quality assurance

The imaging protocol will consist of sequences recommended by the European society of urogenital radiology (ESUR) and their prostate imaging reporting and data system (PI-RADS v. 2.1 (<https://www.acr.org/-/media/ACR/Files/RADS/Pi-RADS/PIRADS-V2-1.pdf>)) assessment (86,87). Minor adaptations specific to radiotherapy planning, such as axial sequences without tilting, will be decided by the imaging group, with the insights gained from the FLAME trial and capabilities of each centre taken into consideration (88). To ensure the proper sequences are taken and optimised to the highest quality on each centre's MR or PET/MR scanner, the MR physicist will visit each site to set-up the MR protocol. The images will be optimised after the priorities set within the imaging working group, between the MR specialised radiologists and MR physicist. Once the optimization is complete, the images will be sent for review and approval of the MR radiologists and adjusted accordingly until met with unanimous approval.

The geometric stability of the MR scanners at all radiotherapy sites in Denmark has been investigated and evaluated by the national interdisciplinary network for quality assurance of MR images in radiotherapy (NIMBUS) (89). Further measurements will be performed to minimise and quantify the size of the artefacts around the implanted gold markers, which are required for RT treatment. The results will be shared with the physicists for consideration in choice of PTV margins and with physicians for consideration in delineation uncertainty of the intraprostatic tumour.

PSMA-PET/CT is an implemented procedure in Denmark and Danish Centers more than fulfil the requirements of the EARL PET/CT Accreditation User Manual (https://earl.eanm.org/wp-content/uploads/2023/05/EARL_Manual_4.2.pdf). PSMA-PET/CT is done as a part of the standard procedures in the participating patients, but not a tested procedure in this study, therefore no additional QA is done regarding this procedure.

PSMA-PET/MRI is an add-on procedure in this study and the use of PSMA-PET/CT will be developed in this trial.

Delineation and dose planning quality assurance

In order to assure the greatest level of consistency across participating institutions a workshop will be held January 2025 to establish and train consensus guidelines for target and OAR delineation. The workshop will use data from the prospective trial at Rigshospitalet (Ethical approval: VMK case nr. 2303938 approved 21/06-2023) including multiparametric or PSMA PET/MRI before the start of hormone treatment and at the start of RT and 3 months later. The consensus workshop will follow the model used by other multidisciplinary groups in Denmark using the available infrastructure (82,84,85,90). The inter- and intraobserver variability in delineation will be assessed, and guidelines written based on these results and consensus at the workshop.

Image guidance and adaptive strategies

When applying a normo-fractionated RT schedule daily variations in e.g. rectal or bladder filling are often negligible due to the sheer number of treatments. However, in a hypo-fractionated regime - especially when combined with a boost volume - these variations have much greater impact. Hence, daily imaging is a necessary requirement to monitor such changes. This also means that in addition to a thorough patient specific QA program all participating centers must have a comprehensive and well documented program for adaptation to systematic anatomical changes. Procedures must be in place to monitor variations on a daily basis and identify cases that pose a potential risk of too high doses to organs at risk and/or low doses to target volumes. Furthermore, the procedures must include methods to evaluate the dosimetric impact of the anatomical variations and finally methods to mitigate unacceptable instances. Each participating center must submit its daily imaging and adaptive strategies to the QA group for evaluation and feedback.

AQA group as described above will evaluate the contouring of the focal boost contouring and dose planning before starting the patient's first treatment.

Plan delivery quality assurance

Before enrolling patients in the protocol, each participating centre must complete a validation "dummy run" to verify the accuracy of the delivered dose. This validation requires dose planning on a test case with a delineation of a focal boost, along with patient-specific QA measurements for the delivered dose. Centres may use their standard patient-specific QA devices for these measurements, which involve two evaluations: (a) a general assessment of the total dose delivered and (b) a precise evaluation of the dose delivered specifically to the prostate area, including the focal boost, with stereotactic accuracy (91).

QA measurements should follow AAPM Task Group 218 methodologies (92), such as:

- Conducting IMRT QA measurements using True Composite (TC) or Perpendicular Field-by-Field (PFF) if TC is unsuitable,
- Analysing dose measurements against the corresponding dose plan doses in absolute dose mode, using a threshold for excluding low-dose areas,
- Variations of the detector response as well as of the accelerator output should be factored out of the analysis.

To pass the dummy run, QA analysis must achieve:

- A $\geq 95\%$ pass rate for $\gamma_{3\%,2\text{mm}}$ with a 10% dose threshold for overall dose evaluation,
- A $\geq 95\%$ pass rate for $\gamma_{3\%,1\text{mm}}$ with a 10% dose threshold specifically for the prostate area including the focal boost (stereotactic accuracy).

Different QA approaches may be used for these two evaluations, and each centre must submit a documentation of its QA procedure as well as a detailed evaluation of the test case to the QA group.

Appendix B: Dose constraints

Table 1 below shows isotoxic dose constraints to organs at risk. The Equivalent Dose at 2 Gy fractions known from the conventional 39-fraction treatment regime have been converted to equivalent doses for the two hypo-fractionated schemes using an α/β -value of 3.

Requirements for target coverage for the two hypo-fractionated schemes are listed in table 2. Both tables include priorities designating in which order specific constraints should be fulfilled in case of conflicts between target and OAR. CTVs and certain OARs both have priority 1. This should not lead to conflicts since there are no overlaps between the two.

Table 1

OAR	Normo-fractionated DVH constraint	EQD2 of physical dose	Isotoxic dose: 20 fractions ($\alpha/\beta = 3$)	Isotoxic dose: 12 fractions ($\alpha/\beta = 3$)	Priority
Rectum	$V_{75\text{Gy}} < 2\text{cm}^3$	74 Gy	60 Gy	50 Gy	1
	$V_{70\text{Gy}} < 10\%$	67 Gy	55 Gy	46 Gy	3
	$V_{50\text{Gy}} < 60\%$	43 Gy	46 Gy	31 Gy	3
Urethra	$D_{0.1\text{ccm}} < 85\text{Gy}$	88 Gy	71 Gy	59 Gy	1
	$D_{1\text{ccm}} < 80\text{Gy}$	81 Gy	65 Gy	54 Gy	1
Bowel Bag	$D_{\text{max}} < 78\text{Gy}$	78 Gy	63 Gy	53 Gy	1
Bowel Bag - PTV_5mm	$V_{30\text{Gy}} < 450\text{cm}^3$	23 Gy	20 Gy	18 Gy	3
	$V_{45\text{Gy}} < 195\text{cm}^3$	37 Gy	32 Gy	28 Gy	3
Bladder	$D_{\text{mean}} < 62\text{Gy}$	57 Gy	47 Gy	40 Gy	3
	$V_{80\text{Gy}} < 15\%$	81 Gy	65 Gy	54 Gy	3
	$V_{70\text{Gy}} < 35\%$	67 Gy	55 Gy	46 Gy	3
Femoral Heads	$D_{2\%} < 55\text{Gy}$	48 Gy	41 Gy	35 Gy	3
Body (outside PTVs)	$D_{2\%} < 83\text{Gy}$	85 Gy	67 Gy	56 Gy	3

Table 2

Target volume (X denoting specific dose scheme)	DVH constraint		Priority
	20 fractions	12 fractions	
GTVp_FB_post_X	$D_{\text{mean}} = 75 \text{ Gy} (\pm 1\%)$	$D_{\text{mean}} = 60 \text{ Gy} (\pm 1\%)$	2
GTVp_FB_post_X	$V_{71.25\text{Gy}} > 99.5\%$	$V_{57\text{Gy}} > 99.5\%$	2
CTVp_FB_final_X	$V_{71.25\text{Gy}} > 95\%$	$V_{57\text{Gy}} > 95\%$	3
CTVp_FB_final_X	$D_{0.1\text{ccm}} > 80.25\text{Gy}$	$D_{0.1\text{ccm}} > 64.2 \text{ Gy}$	3
CTVp_X	$V_{57\text{Gy}} > 99.5\%$	$V_{47.5\text{Gy}} > 99.5\%$	1
CTVp_SV_X (T3b)	$V_{57\text{Gy}} > 99.5\%$	$V_{47.5\text{Gy}} > 99.5\%$	1
CTVp_SV_X ($\leq T3a$)	$V_{42.75\text{Gy}} > 99.5\%$	$V_{35.15\text{Gy}} > 99.5\%$	1
CTVn_E_X	$V_{42.75\text{Gy}} > 99.5\%$	$V_{35.15\text{Gy}} > 99.5\%$	1
PTVp_X	$V_{57\text{Gy}} > 98\%$	$V_{47.5\text{Gy}} > 98\%$	2
PTV_SV_X (T3b)	$V_{57\text{Gy}} > 98\%$	$V_{47.5\text{Gy}} > 98\%$	2
PTVn_E_X	$V_{42.75\text{Gy}} > 98\%$	$V_{35.15\text{Gy}} > 98\%$	2

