- Dose constraints for organs at risk are kept according to guidelines in this protocol
- Guidelines for IGRT according to institutional protocol.
- Treatment is delivered with institutional protocols that fulfil the goals and constraints given in this protocol (appendix B).

Radiotherapy

Radiotherapy planning:

Modern RT planning is wholly dependent on high level computing. This allows for creation of highly personalised dose plans with several different dose levels within the same plan. Additionally, these plans exhibit sharp dose gradients towards critical organs at risk (OAR). Depending on treatment modality plans will either use a simultaneously integrated or sequential boost. In the former case the treatment session delivers a boost to the intraprostatic lesion (if randomised for boost) in addition to the prescribed doses to prostate and elective targets. In the latter case prescribed doses to prostate and elective targets are delivered in the same treatment sessions whereas a boost will be delivered in separate sessions using specialised equipment e.g. an MR-Linac. In either case the dose planning will seek to minimise the trade-off between sufficient target coverage - usually between 95% and 107% of the prescribed target doses - and reducing as much as possible the doses to OAR. It is not uncommon that requirements for target and OAR doses are mutually exclusive. The order in which every dose requirement should be prioritised is detailed in Appendix B as well as specific

requirements to target coverage. To ensure that the dose planning of all participating centres will be vetted as part of the comprehensive RT-QA program described in Appendix A.

Rectal and bladder preparation protocol:

Patients should be treated with a comfortably filled bladder and an empty rectum/bowel according to local protocol. Use of Image Guided Radiotherapy (IGRT) is mandatory to ensure the elective target coverage and to assess bladder- and rectal filling. Application of a bladder-filling protocol in an attempt to decrease the volume of bladder irradiated is recommended using IGRT to check the target positioning.

Target volume definition, dose and fractionation:

Delineation of the targets are performed on the treatment planning MRI, guided by both the diagnostic multiparametric MRI (mpMRI) and PSMA-PET CT scan. Organs at risk (OARs) are delineated on the planning CT scan.

Fractionation:

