Seminal Vesicles (SV): If T3b disease, the entire seminal vesicle volume bilateral should be included in the CTVp_SV and treated to a high dose. If \leq T3a, only the proximal 2 cm of the seminal vesicle bilateral should be included in the CTVp_SV and treated to an elective dose. See appendix E

Organ at risk (OAR): will be contoured according to national guidelines.

Organs at risk

The prostate is situated adjacent to both the rectum and urinary system which risks gastro-intestinal (GI) and genitourinary (GU) adverse effects. The FLAME trial showed that long term side effects of conventional prostate RT even when combined with a mildly fractionated intra-prostatic boost are generally modest in frequency and severity (28). However, the addition of an extremely hypofractionated boost close to organs at risk approaches the realm of brachytherapy where very high point doses directly adjacent or even in the organ can lead to very severe adverse effects. The HypoFLAME trial (75) demonstrated that such an approach leads to only low frequencies of grade 2 side effects and very rarely grade 3. The results rely on the treatment being isotoxic i.e. maintaining pre-existing dose constraints of equivalent dose in the specific hypofractionated scheme. Table 1 in appendix B details the isotoxic dose constraints for the relevant organs at risk for each trial arm while Table 2 details the requirements for target coverage.

Study procedures

Identification and information of eligible patients

Eligible patients will be identified and discussed by doctors at the regional multidisciplinary team conference (MDT). Data from the medical record for eligibility screening are handed over to the researcher (name and CPR number of patients to receive radiotherapy, and diagnosis, i.e. cancer of the prostate/DC61.9). Other study relevant data are retrieved only after written consent. All patients

referred for RT who meet the inclusion criteria will be recorded on a screening list. Neoadjuvant and adjuvant ADT will follow Danish national guidelines, which currently include 3 months LHRH agonist or antagonist prior to the start of radiotherapy

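### Appendix B Table 1: the 20- and 12-fraction dose limits miss the table's own EQD2 in 9 of 13 rows, and the priority-1 urethra D0.1ccm limit is about 5 Gy EQD2 too loose

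*Protocol*

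**What the plan says.** Appendix B introduces the table with "Table 1 below shows isotoxic dose constraints to organs at risk". It takes limits "known from the conventional 39-fraction treatment regime" and says they were "converted to equivalent doses for the two hypo-fractionated schemes" at an α/β of 3. Each row of Table 1 gives the conventional limit, its EQD2, a 20-fraction dose, a 12-fraction dose and a priority.

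The body of the protocol makes these limits binding. Under Treatment related procedures: "Dose constraints for organs at risk are kept according to guidelines in this protocol". The same list requires institutional protocols to satisfy Appendix B. The Organs at risk section says the low toxicity in the cited stereotactic focal-boost trial depended on "maintaining pre-existing dose constraints of equivalent dose in the specific hypofractionated scheme", and continues: "Table 1 in appendix B details the isotoxic dose constraints for the relevant organs at risk for each trial arm".

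**The concern.** The formula, the α/β and the target EQD2 are all printed, so every converted dose can be checked. If a converted dose does not return the EQD2 in its own row, the limit is not isotoxic in the protocol's sense, and planners work to a threshold other than the one stated.

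A limit that is too tight costs planning freedom. A limit that is too loose costs protection, and it matters most for a priority-1 organ next to the boost. The urethra is that organ: the background section links reduced toxicity to urethral sparing in particular, and the Potential risks section promises that urethral dose in the boost arm stays at the non-boost level. A row that differed between 12 and 20 fractions could also affect the toxicity comparison in the fractionation trial.

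**Working it through.** **Inputs**, all from Appendix B: α/β = 3; 39 fractions for the conventional limits; 20 and 12 fractions for the converted ones; the 13 rows of Table 1.

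**Formulae.** EQD2 = D × (D/n + 3)/5. The dose in n fractions with a given EQD2 is D = n × (−3 + √(9 + 20 × EQD2/n))/2.

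**Step 1: reproduce the EQD2 column (n = 39).** In row order the formula gives 73.8, 67.1, 42.8, 88.1, 80.8, 78.0, 22.6, 37.4, 56.9, 80.8, 67.1, 48.5 and 85.1. The printed values are 74, 67, 43, 88, 81, 78, 23, 37, 57, 81, 67, 48 and 85. All agree within about 0.5 Gy, so this is the protocol's own formula.

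**Step 2: convert the printed doses back to EQD2.** Urethra D0.1ccm as the example:
- 20 fractions: 71 × (71/20 + 3)/5 = 71 × 6.55/5 = 93.0
- 12 fractions: 59 × (59/12 + 3)/5 = 59 × 7.917/5 = 93.4

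The stated EQD2 is 88. The matching doses are 10 × (−3 + √97) = 68.5 Gy in 20 fractions and 6 × (−3 + √155.67) = 56.9 Gy in 12.

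| Row | Priority | Stated EQD2 | Printed 20/12 fx (Gy) | EQD2 of printed doses | Doses matching stated EQD2 (Gy) |
|---|---|---|---|---|---|
| Rectum V75 | 1 | 74 | 60/50 | 72.0/71.7 | 61.1/51.0 |
| Rectum V70 | 3 | 67 | 55/46 | 63.3/62.9 | 57.2/47.9 |
| Rectum V50 | 3 | 43 | 46/31 | 48.8/34.6 | 42.1/35.9 |
| Urethra D0.1ccm | 1 | 88 | 71/59 | 93.0/93.4 | 68.5/56.9 |
| Urethra D1ccm | 1 | 81 | 65/54 | 81.3/81.0 | 64.9/54.0 |
| Bowel bag Dmax | 1 | 78 | 63/53 | 77.5/78.6 | 63.3/52.7 |
| Bowel bag minus PTV V30 | 3 | 23 | 20/18 | 16.0/16.2 | 26.6/23.3 |
| Bowel bag minus PTV V45 | 3 | 37 | 32/28 | 29.4/29.9 | 37.8/32.4 |
| Bladder mean | 3 | 57 | 47/40 | 50.3/50.7 | 51.2/43.2 |
| Bladder V80 | 3 | 81 | 65/54 | 81.3/81.0 | 64.9/54.0 |
| Bladder V70 | 3 | 67 | 55/46 | 63.3/62.9 | 57.2/47.9 |
| Femoral heads | 3 | 48 | 41/35 | 41.4/41.4 | 45.5/38.6 |
| Body | 3 | 85 | 67/56 | 85.1/85.9 | 67.0/55.6 |

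**Step 3: allow for rounding.** A row counts as mismatched only if the EQD2 range for the printed dose ± 0.5 Gy misses the stated EQD2 ± 0.5 Gy. Nine rows fail, each in both columns. The closest is rectum V75: 60.5 Gy/20 gives 72.9 and 50.5 Gy/12 gives 72.8, still below 73.5. For urethra D0.1ccm, even 70.5 Gy/20 gives 92.0, against at most 88.5. Urethra D1ccm, bowel bag Dmax, bladder V80 and body agree.

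**Step 4: could another α/β explain it?** For any positive α/β, EQD2 lies between D and D²/(2n). For bowel V30 at 20 fractions that range is 10 to 20, so the stated 23 is out of reach. The same holds for 8 of the 26 cells: both cells of rectum V50, bowel V30 and bowel V45, and the 20-fraction cells of bladder mean and femoral heads.

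**Step 5: likely cause.** Pass the EQD2 value through the 39-fraction formula a second time, then convert. For urethra D0.1ccm, 85 Gy becomes 88.05, then 88.05 × (88.05/39 + 3)/5 = 92.6, which converts to 70.8 and 58.7 Gy and rounds to the printed 71 and 59. Over the table this reproduces 23 of 26 cells to the Gy; a single conversion reproduces 8. The three exceptions are the two body cells, which fit a single conversion, and the 46 Gy cell for rectum V50, which fits neither (double conversion gives 36.4). At 39 fractions 78 Gy is exactly 2 Gy per fraction, so a second pass leaves it unchanged, loosens limits above it and tightens those below. That is the direction seen in every mismatched row except for the 46 Gy cell.

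**The case against.** The strongest reply concerns weight, not arithmetic. Seven of the nine rows are tighter than stated in both schedules, which protects patients, and those seven agree between schedules within 0.5 Gy. Seven of the nine are priority 3. Of the two priority-1 failures, rectum V75 is on the safe side by only about 1 Gy physical dose. That leaves one hard limit too loose, by about 2.5 Gy (20 fractions) and 2.1 Gy (12 fractions) on 0.1 ccm. Urethra D1ccm is correctly converted and still constrains the organ, and the commitment to hold boost-arm urethral dose at the non-boost level should often keep the ceiling from binding. At 20 fractions the printed 71 Gy is still just under the 71.25 Gy boost coverage level in Table 2.

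Most of this stands and limits the size of the concern. It does not remove it. The protocol does not say how the urethral commitment is enforced, and it does not correct the table. At 12 fractions the matching limit (56.9 Gy) sits at about the 57 Gy boost coverage level, while the printed 59 Gy is 2 Gy above it, so the slack falls where a boosted lesion lies near the urethra. The QA group's review of first boost patients and the dummy run are not described as checking the conversion.

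Two further points are fair. The document does not show which column the physicists intended, so looser and tighter here mean relative to the printed EQD2. The double conversion is an inference from the numbers.

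**Conclusion.** The concern holds and should be fixed. Nine of 13 rows are inconsistent with their own EQD2 beyond rounding, eight of them by about 4 Gy or more. The safety issue is urethra D0.1ccm, looser than stated by 5.0 Gy EQD2 at 20 fractions and 5.4 Gy at 12. The excess is nearly equal in the two schedules, so it does not bias that comparison. No sample size, endpoint or test changes.

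Rectum V50 is the only row that differs materially between schedules. If 46 Gy is applied as printed, the 20-fraction arms have a looser rectal limit (48.8 against 34.6), which could favour 12 fractions on GI toxicity. If the cell should read 36, it gives 34.6 and that concern disappears, although the row still misses the stated 43. The digit may also have been misread from the PDF, so little weight should rest on it until it is checked.

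The conclusion assumes the linear-quadratic EQD2 formula at α/β = 3, which the reproduced EQD2 column supports.

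**What to change.** Recompute both fractionation columns once from the EQD2 column at α/β = 3, starting with urethra D0.1ccm (about 68.5 Gy/20 and 56.9 Gy/12 for EQD2 88). Check the 46 Gy rectum V50 cell against the sponsor's source table; if EQD2 43 is intended, the limits are about 42 and 36 Gy. Where the tighter printed limits are clinically preferred, keep them and restate the EQD2 so that each row is consistent. The sponsor's physicists and clinicians decide which values are intended. The QA group should sign off the corrected table and re-check any plans already approved against it.

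The cost is an amended table and the plan re-check. No new patients or data are needed.
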